12.2 Serious Adverse Events (SAEs)

A serious adverse event (SAE) is defined as an AE which, in the view of the Investigator results in: 1) Death; 2) a life-threatening event (i.e. an event in which the subject was at risk of death at the time of the event; it does not refer to an event which hypothetically might have caused death if it were more severe); 3) inpatient hospitalization of > 24 hours or prolongation of existing hospitalization; 4) a significant disability/incapacity; or 5) a congenital anomaly/birth defect. Other important medical events may be considered SAEs if, in the opinion of the Investigator, they jeopardize the subject or require intervention to prevent one of the other outcomes listed above. Based on prior investigations, we do not anticipate any SAEs related to the study procedures [23-26]

Treatment Emergent Serious Adverse Events (TE-SAEs)

A treatment emergent serious adverse event (TE-SAE) is defined as any serious adverse event for which there is a reasonable possibility that the investigational product caused the adverse event. For the purposes of safety reporting, "a reasonable possibility" means there is evidence to suggest a causal relationship between the study product/procedures and the adverse event.

12.3 Reporting Responsibilities of the Investigator

Safety monitoring and reporting will be conducted in accordance with all university and departmental standard operating procedures (SOP). The study investigators will report to a surgeon monitor (**[name]**) who is not directly involved in the study, and has been delegated by the sponsor to ensure data quality and subject safety. The investigators will conduct continuous reviews of the safety data, keep track of SAEs and TE-SAEs, which will be discussed at research committee meetings once every 3 months.

Common Terminology Criteria for Adverse Events, Version 5 (CTCAE v5.0) will be used to assess severity of adverse events. All grade 3-5 adverse events, regardless of

association with the IP, will be entered into study database and reviewed at research committee meetings. In addition, all SAEs will be entered into research database and reviewed by the surgeon monitor on an ongoing basis. If a death occurs within 30 days of investigational therapy, and is determined to be related to the study, the investigators will notify the Urology Department Chair (**[name]**) within 1 business day. If an increase in the frequency of grade 3 or 4 adverse events is noted in the study, a report will be submitted to the Department Chair at the time the increased rate is identified. If at any time the principal investigator stops enrollment or stops the study due to safety issues, the Department Chair will be notified within 1 business day and a formal letter will be sent to the Department Chair to be received within 10 business days.

13. Statistical Considerations

13.1 Data Analysis Plan

Analysis plan: Continuous data will be analyzed using ANOVA with repeated measures, or student's T-Test (where applicable) in order to compare differences between the treatment and control groups. For categorical data, Fisher's Exact test to determine differences between groups. Statistical significance will be evaluated using $\alpha=0.05$.

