- The percentage of subjects in each group who attain MCID in IIEF-EF domain from baseline to 12 & 24 weeks after final treatment.
- The difference between groups in change of IIEF-EF score from baseline to 4, 12, & 24 weeks after final treatment.

- Differences in Doppler ultrasound parameters (PSV and EDV) from baseline to 24 weeks after final treatment.

4.3 Secondary Endpoints (safety):

- Incidence of adverse events in all patients during the study period. Anticipated adverse events that will be recorded at every visit are the following
 - o Pain
 - o Bruising
 - o Swelling
 - o Edema
 - o Allergy
 - o Penile Fracture
 - o New Penile Curvature

4.4 Exploratory Endpoints:

- Change in stretched penile length from baseline to 24 weeks after final treatment.
- The percentage of subjects in each group who attain MCID in IIEF-EF domain from baseline to 4 weeks after final treatment.

5. Study Location

The study will be funded by the Department of Urology and coordinated by the University of Miami (UM), Miller School of Medicine, Department of Urology. The UM Interdisciplinary Stem Cell Institute (ISCI) will also support the project (logistics, quality control, management, storage of specimens and data). All study visits will be carried out in the Department of Urology clinics, (ADDRESS: [name], University of Miami Miller School of medicine, Miami, FL. & Lennar address) PRP preparation will take place in the clinic's andrology lab.

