5.1 Additional Study Sites

No additional study sites.

6. Study Population

80 males with ED of organic origin. All patients will be regular PDE5i users/responders. After a 1-month wash-out period for PDE5i, men with ED will be evaluated by IIEF-EF domain and eligible patients will be randomized to one of 2 treatment groups with an equal allocation ratio (1:1). Participants who do not adhere to the 1-month wash-out period, or do not meet the IIEF-EF domain score will be considered a screen failure and will not receive the study therapy.

6.1 Inclusion criteria: In order to participate in this study, a patient must:

- 1) Be Male
- 2) Be 30 to 75 years of age (inclusive).

- 3) Be able to provide written informed consent.
- 4) Have a diagnosis of ED due to organic origin for at least 6 months prior to consent.
- 5) Sexually active in a stable, heterosexual relationship of more than three months duration.
- 6) IIEF-EF score 11-25 at screening (even if taking a single PDE5).
- 7) Agree to attempt sexual intercourse at least 4 times per month for the duration of the study without being under the influence of alcohol or recreational drugs.
- 8) Agree to comply with all study related tests/procedures.

6.2 Exclusion criteria: In order to participate in this study, a patient must not:

- 1) Previous penile surgery of any kind (except circumcision and condyloma removal), such as penile lengthening, penile cancer surgery, penile plication, grafting.
- 2) Previous history of priapism or penile fracture
- 3) Abnormal morning serum testosterone level defined as a value lower than 300 ng/dL ($\pm 5\%$) (indicative of untreated hypogonadism), or greater than 1197 ng/dL ($\pm 5\%$).
- 4) Current or previous hormone usage, other than prescribed testosterone, clomiphene or thyroid medication. (Subjects with prior or current use of hormonal treatment for prostate cancer are also excluded.
- 5) Psychogenic ED as determined by study investigator.
- 6) Anatomical (Peyronie's Disease or penile curvature that negatively influences sexual activity) or neurological abnormalities in the treatment area.
- 7) Patients using ICI for management of ED
- 8) Patients with generalized polyneuropathy, or neurological conditions irrespective of cause, such as severe diabetes, multiple sclerosis or Parkinson's disease.

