8.2 Description of Study Procedures

8.2.1 *Informed Consent:* Refer to Section 7.3 for details regarding the informed consent process. Study procedures will be completed only after participants have signed the informed consent documentation.

8.2.2 *Demographics:* Demographic characteristics will be recorded including: date of birth, gender, marital status, race and ethnicity. If Medical history has been recorded as part of their participation in another study those source documents may be requested and used for the purpose of this research study.

8.2.3 *Medical History:* Assessment of current and past medical, surgical, and social history will be conducted.

8.2.4 *Physical Examination:* Genitourinary/Reproductive system physical exam will be performed.

8.2.5 *Doppler Ultrasound:* Penile Doppler ultrasound will be performed as standard of care for the management of erectile dysfunction. Results from within the past 12 months can be extracted from the medical record for use in this study.

8.2.6 *Concomitant Medications:* Review of current use of prescription and over the counter (OTC) medications. Participants must discontinue use of PDE5i medications throughout the duration of the study.

8.2.7 *Review Adverse Events:* Refer to Section 12 for description and reporting of adverse and serious adverse events

8.2.8 *Randomization:* Refer to Section 9.3 for details about randomization plan

8.2.9 *Study Therapy Injection:* Approximately 120mL of blood will be collected from participants for preparation of investigational product. Refer to Section 9.2 for description of IP preparation and administration.

8.2.10 *International Index of Erectile Function (IIEF) Questionnaire:* This validated 15-item self-evaluation scale provides pre and post treatment clinic evaluations of erectile function, orgasmic function, sexual desire, satisfaction in sexual intercourse and general satisfaction. If the subject has completed the IIEF questionnaire within the past 6 months, those results may be requested and used for the purpose of this research study. Questionnaires will be completed prior to therapy at injection visits.

8.2.11 *Sexual Encounter Profile (SEP3) Questionnaire:* This 5-item questionnaire is completed after each sexual intercourse attempt. Participants will be asked to complete the short version consisting of question #2 and #3 only.

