8.3.2 Visit 2-3: Injection Visits (Day 0 & Day 28)

All participants will complete the IIEF questionnaire, and SEP diaries will be evaluated. Upon evaluation of eligibility, subjects will be randomized to one of the 2 parallel study groups, using an online program, and initiate treatment on the same day.

There will be 2 treatment visits for all Groups with 28 ± 7 days treatment interval for all subjects. Subjects will complete a Visual Analogue Scale (VAS) pain score after the end of each treatment. Refer to table 1 for all procedures to be performed at the Intervention Visits.

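### The continuous secondary endpoints are analysed without baseline adjustment, and repeated-measures ANOVA, if used, discards observed IIEF-EF scores; a mixed model and ANCOVA would regain precision without more patients.

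*Combined protocol and SAP*

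**What the plan says.** Section 13.1 is the whole analysis plan. It reads "Continuous data will be analyzed using ANOVA with repeated measures", with the alternative of a Student "T-Test (where applicable) in order to compare differences between the treatment and control groups". Fisher's exact test is named for categorical data and alpha is 0.05. The section does not say which continuous endpoint gets which test. Neither it nor any other section names a baseline covariate, an analysis population or a missing-data method.

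The endpoints concerned are in Section 4.2: "The difference between groups in change of IIEF-EF score from baseline" to weeks 4, 12 and 24, and "Differences in Doppler ultrasound parameters (PSV and EDV) from baseline to 24 weeks after final treatment". Both are changes, so baseline enters by subtraction only.

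The baseline may be old. For the IIEF, Section 8.2.10 says: "If the subject has completed the IIEF questionnaire within the past 6 months, those results may be requested and used". For the Doppler scan, Section 8.2.5 says: "Results from within the past 12 months can be extracted from the medical record for use in this study". A current IIEF is also planned. Section 6 has men assessed after the PDE5i wash-out, and Section 8.3.2 says of the injection visits: "All participants will complete the IIEF questionnaire, and SEP diaries will be evaluated". No section says which of these scores is the baseline.

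Section 13.2 allows for about 20% attrition among 80 men.

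**The concern.** There are two separate issues.

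**Weight on baseline.** A change score subtracts baseline with a weight of 1. That weight is the best one only under a particular relation between the correlation and the two SDs (see the working). If the correlation is weaker than that, subtraction adds noise. An IIEF up to 6 months old or a Doppler up to 12 months old makes a weak correlation more plausible. The price is precision, not validity: randomisation keeps the change-score comparison unbiased, but the estimates are wider than the collected data require.

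**Incomplete rows.** Classical repeated-measures ANOVA needs a score at every visit. A man who gives a week-4 score and then leaves is dropped from the week-4 comparison too. That also loses precision. It can bias the IIEF-EF comparison when dropout depends on outcome and does so differently in the two arms. Doppler has one follow-up scan, so this second issue does not arise there.

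**Working it through.** The plan gives no power or precision figure for the continuous endpoints, so there is none to reproduce. The sample size in Section 13.2 concerns the responder endpoint only.

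**1. Gain from adjusting for baseline**

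Set the follow-up SD to 1 and the baseline SD to k, with correlation rho. Both k and rho are assumed, because the documents give neither.

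- Variance of the change score: 1 + k² − 2·rho·k
- Variance after adjustment: 1 − rho²
- Difference: (k − rho)², so a weight of 1 is optimal only when rho = k
- Extra patients that adjustment is worth: (1 + k² − 2·rho·k)/(1 − rho²) − 1

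Example, k = 1 and rho = 0.3: the variance ratio is 0.91/1.40 = 0.650, and 1/0.650 − 1 = 54%.

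| Variance ratio, adjusted/change (extra patients) | rho 0.1 | rho 0.3 | rho 0.5 | rho 0.7 |
|---|---|---|---|---|
| k = 1 | 0.550 (82%) | 0.650 (54%) | 0.750 (33%) | 0.850 (18%) |
| k = 0.8 | 0.669 (50%) | 0.784 (27%) | 0.893 (12%) | 0.981 (2%) |
| k = 0.6 | 0.798 (25%) | 0.910 (10%) | 0.987 (1%) | 0.981 (2%) |

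Entry is limited to an IIEF-EF of 11–25 (Section 6.1), which makes k below 1 likely for that endpoint. PSV and EDV have no entry limit. The rho = 0.1 column represents an old baseline.

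Estimating one slope costs about 1/(n − 4): 1/76 = 1.3% with 80 men and 1/60 = 1.7% with 64. At k = 0.6–0.8 with high rho, the net gain is therefore close to zero.

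**2. Scores lost under complete-case ANOVA**

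Attrition of 20% of 80 is 16 men, leaving 64 completers. Complete-case ANOVA uses 3 × 64 = 192 scores.

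| When the 16 leave | Scores observed | Discarded |
|---|---|---|
| All before week 4 | 64 + 64 + 64 = 192 | 0 |
| Evenly before weeks 4, 12 and 24 | 74.7 + 69.3 + 64 = 208 | 16 (about 11 at week 4, 5 at week 12) |
| All after week 12 | 80 + 80 + 64 = 224 | 32 |

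**3. Possible bias under complete-case ANOVA**

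Assume no treatment effect, normal scores, follow-up SD 1, equal pairwise correlations rho of 0.3–0.7, and k of 0.8–1. After week 4, a fraction p of men in the lower half of week-4 change drop out, so p/2 of the arm is lost. Let s = √(1 + k² − 2·rho·k) be the SD of change.

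- Mean week-4 change among completers is shifted by 0.3989·p·s/(1 − p/2).
- Dropout of 20% in both arms (p = 0.4): the shift is the same in each arm and cancels.
- Dropout of 30% on placebo (p = 0.6) and 10% on PRP (p = 0.2): the shifts are 0.342s and 0.089s, a difference of 0.253s against PRP.
- Week 4: s runs from 0.721 (k = 0.8, rho = 0.7) to 1.183 (k = 1, rho = 0.3), so the bias is 0.18 to 0.30 SD.
- Week 24: multiply 0.253s by (rho + k² − 2·rho·k)/s². The bias runs from 0.253 × 0.22/0.721 = 0.08 SD to 0.253 × 0.70/1.183 = 0.15 SD.

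A simulation with 400,000 men per arm agrees: 0.183–0.300 SD at week 4, 0.080–0.149 SD at week 24, and at most 0.004 SD at week 24 when the dropout pattern is the same in both arms. Regressing week 24 on baseline and week 4 within arm, a stand-in for a likelihood analysis under missing at random, left at most 0.004 SD in both scenarios.

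**The case against.** The strongest reply is that this is an optimisation of secondary endpoints in a trial labelled a pilot. The planned tests are valid, they match the endpoints as worded, and no power is claimed for them. That is correct, and it limits the weight of the point.

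The size of the gain is also uncertain. Rho and k are assumed and the results run from about 1% to 82%. For IIEF-EF, where k below 1 is likely, the k = 0.6–0.8 rows at rho 0.3–0.7 give 1–27% before the slope cost. The old-baseline case is weaker for IIEF-EF than for Doppler, because a current pre-treatment score is planned. All of this stands. What remains is a gain that ranges from negligible to large, against a loss of at most about 1.7%.

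The plan does not say that men with missed visits are dropped, and a t-test at each visit would keep them. This stands too, so the second issue depends on the test chosen. But Section 13.1 names repeated-measures ANOVA first and leaves the choice open.

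The 30% v 10% dropout split is illustrative; the documents give only the overall 20%. Even one dropout rule shared by both arms gives a small attenuation (about 0.04 SD at week 4 and 0.02 SD at week 24) if PRP has an assumed 0.5 SD effect. The reason is that fewer PRP men then meet the rule, so dropout again differs by arm (about 20% v 10–13%).

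Finally, the missing analysis population also leaves open how a man without a week-4 IIEF counts in the primary analysis. That is true, but it is a separate matter from the covariate and the ANOVA.

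**Conclusion.** The point holds and should be acted on, as a matter of precision in secondary endpoints. No validity problem follows from omitting the covariate. At rho 0.3–0.7, adjustment is worth 18–54% more patients if k = 1, 2–27% if k = 0.8 and 1–10% if k = 0.6, with a net gain near zero at the lower ends of the last two ranges. At rho = 0.1 it is worth 25–82%. These figures rest on assumed values of rho and k.

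If complete-case ANOVA is used for IIEF-EF, it discards 0 to 32 observed scores, and 16 of 208 if losses are even. It is biased only where outcome-related dropout differs by arm. In the illustrated 30% v 10% case the bias is 0.18–0.30 SD at week 4 and 0.08–0.15 SD at week 24, against PRP. Most of the week-24 gain would come from the covariate: at k = 1 with equal correlations and assumed retention of 95%, 87.5% and 80%, the mixed model reduces variance by only about 1–3% beyond ANCOVA on available data. The primary responder endpoint and its Fisher test are unaffected by these two issues.

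**What to change.** Amend Section 13.1 as follows.

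- **IIEF-EF:** a mixed model for repeated measures on change at weeks 4, 12 and 24, with arm, visit, arm-by-visit, baseline IIEF-EF and preferably baseline-by-visit. Include every randomised man with any post-baseline score, analysed as randomised.
- **PSV and EDV:** ANCOVA at week 24 with the baseline value as covariate.
- **Baseline:** state which pre-treatment IIEF-EF score is used, since Sections 8.2.10, 8.3.1 and 8.3.2 allow a historic, a screening or an injection-visit score.
- **Missing data:** report missed visits by arm.
- **Primary endpoint:** keep Fisher's exact test. A severity-adjusted responder analysis should be supportive at most. It must wait until the MCID bands in Section 13.2, where a score of 16 falls in both bands and scores of 11 and 22–25 in neither, are reconciled with the 11–25 entry range.

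The cost is SAP wording and slightly more analysis work; no new data, visits or patients are needed. The downsides are one estimated slope (about 1.3–1.7% of precision) and a missing-at-random assumption in the mixed model.

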
| Human Studies of PRP for ED | | | | | | | |
|-----------------------------|------|--------------------|---|---|----------|---|---|
| Author | Year | Number of Patients | Patient Population | Administration | Followup | Adverse Events | Conclusion |
| Banno [26] | 2017 | N=9 | Penile Rehab | PRP ICI into Penises with Vacuum Device | 4 weeks | No AEs reported | PRP may represent a safe and viable option as a supplementary therapy for penile rehabilitation. Particularly notable is the prospect of zero side effects. |
| Matz [24] | 2018 | N=16 | Erectile dysfunction, Peyronies Disease | PRP with CaCl ICI | 15.5m | Minor: Bruising 1, Mild Pain 4. Major: none | PRFM injections for ED, PD, and female SUI are feasible and safe. Although the limited data is suggestive of efficacy, a placebo control will be required in subsequent efforts for confirmation |
| Epifanova [25] | 2019 | N=10 | Erectile Dysfunction | 6 injections PRP with CaCl2 and Shockwave | 60 Days | No AEs reported | There were no serious adverse events as well as severe adverse events. Erectile dysfunction symptoms in all men participated in the study significantly decreased after treatment with PRP-therapy and extracorporeal shockwave therapy |
| Alkhayal [23] | 2018 | N=40 | Erectile Dysfunction | 1 injection PRP | >1 month | No AEs reported | Platelet rich plasma is a safe and efficacious option for penile rejuvenation and improvement of erectile dysfunction |

Table 1: Summary of published studies and abstracts

To date, there are no treatments that address the underlying cause of endothelial dysfunction, although LIST treatment for ED has shown promising results. Platelet-derived therapies targeting inflammation and promoting tissue/nerve regeneration and may represent a potential treatment option towards this direction. Despite growing evidence to the efficacy of PRP, no randomized placebo-controlled studies exist.

3. Study Objectives

3.1 Primary Objective:

To investigate and compare the treatment efficacy of PRP vs placebo treatment in men with mild-moderate ED, as measured by IIEF.

3.2 Secondary Objective:

To study the adverse events and safety of the PRP treatment in men with mild-moderate ED, as measured by IIEF.

4. Study Endpoints

4.1 Primary Endpoint:

- The percentage of subjects in each group who attain MCID in IIEF-EF domain from baseline to 4 weeks after final treatment.

4.2 Secondary Endpoints (efficacy):

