13.2 Sample Size

Inclusion Criteria are men with IIEF scores >11 which includes men with mild (IIEF 16-21) and mild/moderate (12-16) Erectile dysfunction. Minimal clinically important differences (MCID) for these groups are an increase of 2 for mild and 5 for moderate ED. Previous studies on the effect of placebo show about a 15% improvement in men with mild to moderate ED. Therefore, 15% of the placebo group is expected to meet MCID. Results from the PRP safety study by Matz et al. 2018, which showed a mean improvement in IIEF of 4.14 points in seven patients with ED after PRP. In the interventional group, we expect 50% to meet MCID. At 80% power, we will therefore need 30 patients in each group to detect a difference of 35% between treatment and placebo arms.

$$\text{Sample size} = \frac{2(Z_{\alpha/2} + Z_{\beta})^2 P(1 - P)}{(p_1 - p_2)^2}$$

$$28.08 = (2*(1.96+0.84)^2 * (0.25*(1-0.25)) / (0.35^2)$$

Assuming attrition of approximately 20%, an additional 6 participant slots will be added to each group for a total sample size of 80 subjects.

14. Risks to Subjects

We anticipate there to be few adverse events related to the study. Based on the four published studies and abstracts, including 75 men, only minor adverse events were reported (Bruising 1, Mild Pain 4). No serious adverse events were observed [23-26] (Table 2). After literature review, we believe this product to be of non-significant risk to patients (NSR) and for investigational use in a clinical study protocol.

Based on published studies, we will record anticipated adverse events to patients include: local injection site reaction, penile pain and penile bruising. Additionally, we anticipate

patients may experience, penile swelling, allergic reaction, local infection (though none reported in previous studies) and will record them at every visit systematically.

15. Potential Benefits to Subjects

The potential benefits for men randomized to the treatment arm will include improvement in erectile function and sexual performance.

16. Privacy & Confidentiality

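### Section 13.1: Fisher's exact test is valid for the responder endpoints but spends well under its 0.05 with equal arms; Boschloo's test, ordered on the two-sided Fisher p-value, recovers power at no cost in patients

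*Combined protocol and SAP*

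**What the plan says.** Section 13.1 gives one rule for all categorical outcomes: "For categorical data, Fisher's Exact test to determine differences between groups. Statistical significance will be evaluated using $\alpha=0.05". The significance level is 0.05. Sidedness is not stated, and neither the conservatism of the test nor any alternative is discussed.

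The rule governs the main result, because the primary endpoint in Section 4.1 is binary: "The percentage of subjects in each group who attain MCID in IIEF-EF domain from baseline to 4 weeks after final treatment". The same responder measure at weeks 12 and 24 is a secondary endpoint in Section 4.2.

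Section 13.2 sizes the trial with a normal-approximation formula, not with Fisher's test, and concludes: "At 80% power, we will therefore need 30 patients in each group to detect a difference of 35% between treatment and placebo arms". The synopsis and Section 8 give 40 subjects per group, and Section 13.2 assumes about 20% attrition. Section 9.3 describes a computer-generated 1:1 sequence and mentions no blocking.

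**The concern.** The design fixes the two arm sizes but not the total number of responders. Fisher's test conditions on that total as well. With 30 to 40 men per arm, few tables are then possible for a given total, so the attainable p-values are coarse and the test often cannot come close to 5%. An unconditional exact test on the same table can use more of the stated level while still guaranteeing it.

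What is at stake is power on the primary endpoint and the two later responder endpoints. The sample-size formula takes no account of this loss, so the planned test may fall short of the power quoted for it. The choice can also decide a borderline result. With 14/40 versus 6/40 responders, Fisher gives p = 0.069 and Boschloo p = 0.045. The test therefore cannot credibly be chosen after the data are seen.

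**Working it through.** **Inputs.** The level is 0.05 (13.1). It is taken as two-sided because 13.2 uses 1.96. For placebo, 13.2 states: "Therefore, 15% of the placebo group is expected to meet MCID". For PRP: "In the interventional group, we expect 50% to meet MCID". Size before attrition is 30 per arm, attrition about 20% (13.2), and planned enrolment 40 per arm (synopsis, Section 8).

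**The plan's own figure.** The formula is 2(1.96 + 0.84)² P(1 − P)/(p₁ − p₂)². With P = (0.15 + 0.50)/2 = 0.325 it gives 2 × 7.84 × 0.325 × 0.675 / 0.1225 = 28.08, as stated. The printed substitution, "28.08 = (2*(1.96+0.84)^2 * (0.25*(1-0.25)) / (0.35^2", shows P = 0.25, which would give 24.0. The result is right and the printed input is not. That is a separate matter and does not affect what follows.

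**Method.** Every 2×2 table was enumerated for each pair of arm sizes.
- Fisher rejects when the two-sided (minimum-likelihood) p ≤ 0.05.
- Boschloo, as used here, takes that same p-value as ordering statistic. It uses the largest cut-off whose rejection probability, maximised over the common response rate, is at most 0.05.
- Size and power are exact binomial sums.

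Fisher's cut-off of 0.05 already has maximum size below 0.05, so Boschloo's cut-off cannot be smaller. Its rejection region therefore contains Fisher's by construction, and the enumeration confirmed this in every layout checked.

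**Equal evaluable arms**, power at 50% versus 15%:

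| Per arm | Max size, Fisher | Max size, Boschloo | Power, Fisher | Power, Boschloo | Gain (points) |
|---|---|---|---|---|---|
| 29 | 2.5% | 4.8% | 75.7% | 83.1% | 7.4 |
| 30 | 2.7% | 4.7% | 77.7% | 82.1% | 4.4 |
| 32 | 3.3% | 4.7% | 81.5% | 86.4% | 4.9 |
| 36 | 2.8% | 4.9% | 86.1% | 90.8% | 4.7 |
| 40 | 3.3% | 4.8% | 89.8% | 92.7% | 2.9 |

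Thirty-two is 40 × 0.8. Twenty-nine is 36 × 0.8 = 28.8, rounded, where 36 is the 30 + 6 of Section 13.2.

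**Unequal evaluable arms** (PRP/placebo), same rates:

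| Arms | Max size, Fisher | Max size, Boschloo | Power, Fisher | Power, Boschloo | Gain (points) |
|---|---|---|---|---|---|
| 29/31 | 3.9% | 4.7% | 80.1% | 84.2% | 4.1 |
| 31/29 | 3.9% | 4.7% | 80.9% | 84.7% | 3.8 |
| 30/32 | 4.0% | 4.9% | 81.9% | 85.9% | 4.0 |
| 32/33 | 4.6% | 4.8% | 85.4% | 87.8% | 2.4 |
| 34/38 | 3.9% | 4.9% | 89.8% | 90.5% | 0.7 |
| 38/40 | 4.2% | 4.9% | 90.9% | 92.5% | 1.6 |

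Over all unequal pairs from 24 to 40, Fisher's maximum size runs from 3.4% to 4.6%.

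**If the PRP rate is lower**, say 40% versus 15% (an assumption, not a plan figure), Boschloo against Fisher gives 53.4% against 48.9% at 30 per arm, 67.5% against 58.2% at 36, and 70.0% against 64.1% at 40. With unequal arms the gain can be as small as 0.6 points (34/38).

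**The case against.** The strongest reply is that nothing in Section 13.1 is wrong. Fisher's test holds the error at or below 0.05, is familiar, and is a defensible choice for a trial labelled Phase I and pilot. Conditional and unconditional testing are both recognised approaches. All of that stands.

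The reply also limits the size of the point, in three ways that a reader of the equal-arm table could miss.

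- A reader might infer that the true error rate can never exceed 3.3%. The documents do not support that. With about 20% attrition and no blocking described, equal evaluable arms are unlikely, and the ceiling with unequal arms is 3.4-4.6%. Even an equal split outside the tabulated sizes can exceed 3.3%: at 33 per arm the maximum is 3.56%.
- A reader might infer that the trial is underpowered because of Fisher. The shortfall to 77.7% belongs to exactly 30 per arm. The same 60 men split 29/31 give 80.1% or 80.9%. Enrolment is planned at 40 per arm, and 32 or more evaluable per arm meets 80% under the plan's own rates.
- A reader might infer that any unconditional exact test dominates Fisher. It does not. Doubling a one-sided Boschloo test misses some Fisher rejections in 63 of the unequal pairs from 24 to 40 and can have lower power (24/29: 76.1% against 76.6%). The pooled-Z unconditional test misses two Fisher rejection points at 32/35.

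The reply does not remove the gain itself. In every layout checked, the Boschloo test defined above kept its size below 5% and had higher power than Fisher.

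**Conclusion.** The point holds as a matter of efficiency, not validity. Fisher's test does not breach the stated level; it leaves part of it unused. At 15% versus 50% the recoverable power is about 3-7 points with equal evaluable arms and about 1-4 points with unequal arms. The only planned size at which the choice decides whether the stated 80% is met is the 30 per arm of Section 13.2 with exact balance: 77.7% under Fisher, 82.1% under Boschloo.

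This rests on a two-sided test (inferred from 1.96), the minimum-likelihood form of Fisher's two-sided p-value, and the plan's response rates. The guarantee of never rejecting less often than Fisher applies to Boschloo's test ordered on that two-sided p-value and to no wider class.

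**What to change.** Amend Section 13.1 before unblinding. For the responder endpoints at weeks 4, 12 and 24, specify Boschloo's unconditional exact test, with the two-sided Fisher p-value as ordering statistic, at two-sided alpha 0.05. Report Fisher's p-value as a sensitivity result. State the ordering explicitly and confirm that the software uses it, since other two-sided definitions lose the guarantee. Check the maximum over the common response rate on a fine grid. The amendment also settles the sidedness that 13.1 leaves open.

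The cost is about one sentence, a test less familiar to readers and slightly more computation. No patients and no new data are needed.
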